6.9 Analysis of Safety Data

The summary of safety will be performed based on safety analysis set.

The safety analysis will be based on the reported AEs, clinical laboratory evaluations, physical examination, vital signs, and 12-lead ECG.

6.9.1 Analysis of Adverse Events

Incidence tables for both non-TEAEs and TEAEs will be presented. The table will include the number (n) and percentage (%) of participants who are experiencing an adverse event, along with the corresponding number of episodes of AEs. Participants with multiple adverse events in a particular category will be counted only once in that category. Participants with multiple severities/grading will be counted only once under maximum severity/grading.

The number and proportion of participants reporting non-TEAEs/TEAEs will be summarized, sorted by decreasing frequency of SOC and PT, and in case of further ties, then alphabetically.

Listings will be provided by SOC and PT, for non-TEAEs, TEAEs and TESAEs, TEAEs of infusion related reactions, and TEAEs leading to study treatment discontinuation.

The following summaries will be provided for the adverse events.

- Overall summary of AEs: The overall summary of AEs will be provided with number and proportions of participants with any:
 - non-TEAE
 - TEAE
 - Related TEAE
 - SAE
 - TEAE by CTCAE grades
 - TEAE that are infusion related reaction
 - TEAE leading to 4-week dosing period discontinuation
 - TEAE leading to 12-week dosing period discontinuation
 - TEAE leading to study discontinuation
 - TEAE with outcome of death
- Summary of non-TEAEs by SOC and PT
- Summary of TEAEs by SOC and PT
- Summary of TEAE occurred during treatment period by SOC and PT
- Summary of TEAEs occurring for at least 2 participants by PT
- Summary of Serious TEAEs by SOC and PT
- Summary of TEAEs by PT and worst CTCAE grade
- Summary of TEAEs with CTCAE grade 3 or higher by PT
- Summary of treatment related TEAEs by SOC and PT

6.9.2 Analysis of Clinical Laboratory Measurements

Laboratory measurements include clinical chemistry, hematology and urinalysis results. Summaries of laboratory variables will include:

- Descriptive statistics of continuous laboratory result and change from baseline by visit
- Number (n) and percentage (%) of participants for categorial lab data (urinalysis)
- The number (n) and percentage (%) of participants with abnormal lab value during study using a shift table
- Number (n) and percentage (%) of participants with CTCAE grade for key hematology parameters (white blood cell [WBC], neutrophils, lymphocytes, platelet, and hemoglobin)
- Number (n) and percentage (%) of participants with CTCAE grade for key serum chemistry parameters (alanine aminotransferase [ALT], aspartate aminotransferase [AST], serum creatinine, and bilirubin)

Note: When participants have multiple CTCAE grades within the same parameters, the worst CTCAE grade will be considered. Refer [Appendix 12.8](#) for more details on CTCAE grading.

Listing of all laboratory parameters original results, standard results, normal range, abnormal flag and CTCAE grade (wherever applicable) by participant and visit will be provided. Additionally, listings will be provided for pregnancy test, tuberculosis test, and virology test.

A line graph illustrating absolute values for key parameters will be presented by visit.

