11.3.1 Analysis of Safety

Safety variables including incidence and severity, and duration of TEAEs and changes from baseline of relevant parameters (such as vital signs, ECGs, and clinical laboratory values) will be summarized.

- AEs will be coded using the Medical Dictionary for Regulatory Activities (MedDRA, version currently in use by the Sponsor at the time of database lock). TEAEs are defined as events started after initiation of the first dose of study treatment or events present that worsen after the start of dosing. The number and proportion of participants experiencing one or more TEAEs will be summarized by severity, and relationship to study treatment.
- Prior and concomitant medications (including rescue medications) will be coded using the World Health Organization Drug Dictionary (WHODrug). The number and proportion of participants taking prior and/or concomitant medications will be summarized.
- Vital sign (systolic and diastolic blood pressure, pulse, respiratory rate, and temperature) and ECG parameters will be summarized by visit descriptively. Changes from baseline, number, and proportion of participants with clinically important values will be presented descriptively.
- Clinical laboratory parameters will be summarized using descriptive statistics, by changes from baseline, post-dosing shift from Baseline (Day 1) in the normal or abnormal category of laboratory values by visit, and number and proportion of participants with a treatment-emergent clinically significant abnormal value based on predefined criteria, and data listings.

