12.8 CTCAE Version 5.0 for Key Hematology and Serum Chemistry Parameters

CTCAE Term	Grade 1	Grade 2	Grade 3	Grade 4	Grade 5
White blood cell decreased	<LLN - 3000/mm3; <LLN - 3.0 x 10e9 /L	<3000 - 2000/mm3; <3.0 - 2.0 x 10e9 /L	<2000 - 1000/mm3; <2.0 - 1.0 x 10e9 /L	<1000/mm3; <1.0 x 10e9 /L	-
Neutrophil count decreased	<LLN - 1500/mm3; <LLN - 1.5 x 10e9 /L	<1500 - 1000/mm3; <1.5 - 1.0 x 10e9 /L	<1000 - 500/mm3; <1.0 - 0.5 x 10e9 /L	<500/mm3; <0.5 x 10e9 /L	-
Lymphocyte count decreased	<LLN - 800/mm3; <LLN - 0.8 x 10e9/L	<800 - 500/mm3; <0.8 - 0.5 x 10e9 /L	<500 - 200/mm3; <0.5 - 0.2 x 10e9 /L	<200/mm3; <0.2 x 10e9 /L	-
Anemia	Hemoglobin (Hgb) <LLN - 10.0 g/dL; <LLN - 6.2 mmol/L; <LLN - 100 g/L	Hgb <10.0 - 8.0 g/dL; <6.2 - 4.9 mmol/L; <100 - 80g/L	Hgb <8.0 g/dL; <4.9 mmol/L; <80 g/L; transfusion indicated	Life-threatening consequences; urgent intervention indicated	Death
Platelet count decreased	<LLN - 75,000/mm3; <LLN - 75.0 x 10e9 /L	<75,000 - 50,000/mm3; <75.0 - 50.0 x 10e9 /L	<50,000 - 25,000/mm3; <50.0 - 25.0 x 10e9 /L	<25,000/mm3; <25.0 x 10e9 /L	-
Alanine aminotransferase increased	>ULN - 3.0 x ULN if baseline was normal; 1.5 - 3.0 x baseline if baseline was abnormal	>3.0 - 5.0 x ULN if baseline was normal; >3.0 - 5.0 x baseline if baseline was abnormal	>5.0 - 20.0 x ULN if baseline was normal; >5.0 - 20.0 x baseline if baseline was abnormal	>20.0 x ULN if baseline was normal; >20.0 x baseline if baseline was abnormal	
Aspartate aminotransferase increased	>ULN - 3.0 x ULN if baseline was normal; 1.5 - 3.0 x baseline if baseline was abnormal	>3.0 - 5.0 x ULN if baseline was normal; >3.0 - 5.0 x baseline if baseline was abnormal	>5.0 - 20.0 x ULN if baseline was normal; >5.0 - 20.0 x baseline if baseline was abnormal	>20.0 x ULN if baseline was normal; >20.0 x baseline if baseline was abnormal	
Blood bilirubin increased	>ULN - 1.5 x ULN if baseline was normal; > 1.0 - 1.5 x baseline if baseline was abnormal	>1.5 - 3.0 x ULN if baseline was normal; >1.5 - 3.0 x baseline if baseline was abnormal	>3.0 - 10.0 x ULN if baseline was normal; >3.0 - 10.0 x baseline if baseline was abnormal	>10.0 x ULN if baseline was normal; >10.0 x baseline if baseline was abnormal	
Creatinine increased	>ULN - 1.5 x ULN	>1.5 - 3.0 x baseline; >1.5 - 3.0 x ULN	>3.0 x baseline; >3.0 - 6.0 x ULN	>6.0 x ULN

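### SAP 6.9.2 counts laboratory abnormalities by worst CTCAE grade with no stated post-dose limit or comparison with baseline grade, and no laboratory summary there delivers the protocol's treatment-emergent count

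*SAP*

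**What the plan says.** Protocol 11.3.1, repeated in the synopsis, lists among the laboratory summaries the "number and proportion of participants with a treatment-emergent clinically significant abnormal value based on predefined criteria". It also describes a post-dosing shift from Day 1 between normal and abnormal categories, by visit. Protocol 8.2.3 says laboratory tests will be summarised in the study report by worsening shift from the baseline value.

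SAP 6.9.2 plans five kinds of summary:
- descriptive statistics and change from baseline by visit;
- counts for categorical urinalysis;
- "The number (n) and percentage (%) of participants with abnormal lab value during study using a shift table";
- counts by CTCAE grade for five haematology parameters (WBC, neutrophils, lymphocytes, platelets, haemoglobin);
- counts by CTCAE grade for four chemistry parameters (ALT, AST, creatinine, bilirubin).

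A note on the two grade tables reads: "When participants have multiple CTCAE grades within the same parameters, the worst CTCAE grade will be considered". Neither the note nor the bullets say which visits feed the tables. The section also plans a listing of results with abnormal flag and CTCAE grade by participant and visit, and line graphs of key parameters.

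SAP section 1 says methodological deviations from the protocol are documented. Section 5 documents only the removal of Cohort 2.

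**The concern.** A worst-grade count answers how severe a value ever was. The protocol's treatment-emergent count answers what appeared or worsened after dosing. The two differ whenever a participant enters with a graded value.

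This matters more here than in a controlled trial. Safety is the primary objective, and one open-label group of 13 remains with no placebo, so each participant's own baseline is the only comparator. Lymphocyte count, which bears on the T-cell depletion that the molecule is meant to avoid (protocol 2.4), is among the parameters graded without reference to baseline. The other safety domains in the SAP are handled differently: AEs are split into treatment-emergent and not, and most notable ECG and vital-sign criteria require new onset or a change from baseline. In SAP 9.2, the only laboratory outputs listed for the safety review committee are counts by CTCAE grade.

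**Working it through.** The plan states no figure to reproduce. The check applies the grading rules to a value that does not change after dosing, then asks what the planned tables would show.

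**1. How Appendix 12.8 grades an unchanged entry abnormality.** Haematology is graded on absolute limits; WBC Grade 1, for example, is "<LLN - 3000/mm3; <LLN - 3.0 x 10e9 /L". ALT and AST Grade 1 is "1.5 - 3.0 x baseline if baseline was abnormal", and bilirubin Grade 1 is "> 1.0 - 1.5 x baseline if baseline was abnormal", when baseline is abnormal. An unchanged value has a ratio to baseline of 1.0, which falls outside both bands. Creatinine Grade 1 runs from the ULN to 1.5 x ULN whatever the baseline.

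The example values and lower limits below are assumptions for illustration:

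| Parameter (assumed LLN) | Entry value, unchanged | Grade |
|---|---|---|
| WBC (4.0) | 3.5 | 1 |
| Neutrophils (1.8) | 1.6 | 1 |
| Lymphocytes (1.0) | 0.9 | 1 |
| Haemoglobin (12.0 g/dL) | 11.0 | 1 |
| Platelets (150) | 120 | 1 |
| Creatinine | 1.2 x ULN | 1 |
| ALT or AST | 2.0 x ULN (ratio 1.0) | none |
| Bilirubin | 1.4 x ULN (ratio 1.0) | none |

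So an unchanged abnormality keeps a grade on 6 of 9 parameters. This holds even if only post-dose values enter the table, because the stable value is measured again after dosing. One gap remains in the protected three: ALT at 2.0 x ULN at Screening with a normal Day 1 value (say 0.9 x ULN) is Grade 1 if Screening values enter the table.

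**2. Whether the entry criteria remove such values.** Protocol 5.2, criterion 2, gives numeric Screening limits for ALT/AST, bilirubin and WBC only. The WBC limit excludes values below 3.0, which still admits Grade 1. For the other five of the six parameters, exclusion rests on investigator judgement.

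**3. What the summary tables distinguish**, taking the shift table as normal/abnormal, as in protocol 11.3.1:

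| Baseline to worst post-dose grade | Worst-grade table | Shift table | Worsened? |
|---|---|---|---|
| Normal to 1 | Grade 1 | normal to abnormal | yes |
| 1 to 1 | Grade 1 | abnormal to abnormal | no |
| 1 to 2 | Grade 2 | abnormal to abnormal | yes |
| 2 to 2 | Grade 2 | abnormal to abnormal | no |

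The shift table separates the first pair. Neither table separates the second.

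**4. Size.** One participant is 1/13 = 7.7% of the group. The documents do not give p, the share of participants entering with a grade on any of the six parameters. With p assumed, the expected number is 13p and the chance of at least one is 1 - (1 - p)^13:

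| Assumed p | Expected number | Chance of at least one |
|---|---|---|
| 5% | 0.65 | 48.7% |
| 10% | 1.3 | 74.6% |
| 20% | 2.6 | 94.5% |
| 30% | 3.9 | 99.0% |

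**The case against.** The best defence is that the grade tables are not the only laboratory output. The same section plans a shift table, change from baseline by visit and a listing of grades by participant and visit. With 13 participants, anyone can read from the listing whether a Grade 2 was stable or had worsened. A reader might infer that pre-existing cytopenia cannot be told apart from a drug effect at all; the documents do not support that. What is missing is a summary table that does it.

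Second, the protocol's phrase concerns clinically significant values. Under protocol 8.1.1 and 8.2.3.1 such values are reported as AEs, so those arising after dosing reach the TEAE tables. That covers much of the clinical content, but it depends on investigator judgement, whereas the protocol promises predefined criteria.

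Third, the values that slip through are probably mostly Grade 1. Grade 2 WBC is excluded at Screening, and the investigator may exclude on other laboratory findings. This stands, and it limits the practical harm.

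Fourth, SAP section 6 leaves some table detail to mock shells, which are not in the documents, and Appendix 12.6 keeps Baseline (up to Day 1) as its own analysis visit. The tables may therefore be programmed post-dose only. That would remove pre-dose values but not the stable abnormalities shown in the working.

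**Conclusion.** The point holds as a modest defect in descriptive safety reporting, between minor and should-fix. SAP 6.9.2 states no post-first-dose or worsening rule for its grade tables, none of its laboratory summaries delivers the treatment-emergent count in protocol 11.3.1, and section 5 is silent. A stable entry abnormality can appear as an on-study grade on six of nine parameters, at 7.7 percentage points per participant for that parameter. The number affected is unknown.

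Two stronger readings go too far. A reader might infer that Screening and Day 1 values are counted; the SAP does not say which visits are used, so only that they can be counted is supported. A reader might also infer that 6.9.2 replaces the protocol's summary with the grade tables; the SAP never says so, and they are only the closest match to it.

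The conclusion assumes that all 13 enrolled participants were dosed, that the shift table uses normal/abnormal categories, and that the laboratory commitment read the same in protocol version 6.0, on which the SAP is based, as in the protocol dated 14 June 2024. The primary endpoint, every test and the sample size are unaffected.

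**What to change.** Either of two changes to SAP 6.9.2 closes the gap:

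- define the CTCAE count as participants whose worst grade after the first dose is higher than their baseline grade, with baseline as in SAP 7.1; or
- present, for each of the nine key parameters, baseline grade against worst post-baseline grade.

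The second shows more, since it keeps stable and worsened grades visible side by side, and it fits protocol 8.2.3. A post-dose limit alone is not enough. The same definition should apply to the laboratory counts in SAP 9.2. Section 5 should state how the protocol's treatment-emergent laboratory summary is met, or that it is dropped and why.

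The cost is a few sentences and one restructured table. The data are already collected and graded for the listing.

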6.9.3 Analysis of Vital Signs

Summaries of vital sign variables will include:

- Descriptive statistics of vital sign variables and change from baseline by visits/timepoints
- Notable findings in vital signs will be summarized by visit/timepoint, which are defined as,
 - Temperature: >39.0 degrees
 - An increase in Pulse Rate from baseline by $\geq 25\%$ for on-treatment values >100 beats/min
 - A decrease in Pulse Rate from baseline by $\geq 25\%$ for on-treatment values <50 beats/min.
 - Systolic BP ≥ 140 mmHg and increase by 20 mm Hg.
 - Diastolic BP ≥ 90 mmHg and increase by 10 mm Hg.
 - Systolic BP ≤ 80 mmHg and decrease by 20 mm Hg.
 - Diastolic BP ≤ 50 mmHg and decrease by 10 mm Hg.

A listing of vital signs data will be provided for each participant by visit.

6.9.4 Analysis of 12-Lead ECG

Summaries of 12-lead ECG parameters by visit will include:

- Descriptive statistics of actual and change from baseline.
- ECG status (i.e., normal, abnormal) summarized by a shift table
- Notable findings in ECG, which are defined as:
 - a new onset in the QT interval >500 ms
 - a new onset in the QTcF interval >500 ms
 - an increase from baseline in QTcF >60 ms
 - an increase in heart rate from baseline by $\geq 25\%$ for on-treatment values >100 bpm
 - a decrease in heart rate from baseline by $\geq 25\%$ for on-treatment values <50 bpm
 - an increase in PR interval from baseline by $\geq 25\%$ for on-treatment values >200 ms
 - an increase in the QRS interval from baseline by $\geq 10\%$ for on-treatment values >110 ms, any time on treatment.

A listing will be provided for each participant by visit.

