3 STUDY OBJECTIVES AND ENDPOINTS

Study objectives and endpoints are summarized in [Table 3](#) .

Table 3 Study Objectives and Endpoints

Primary Objective	Primary Endpoint
To evaluate AEs emergent from multiple doses of IMG-007 in adult participants with AD	Incidence of TEAEs
Secondary Objectives	Secondary Endpoints
To evaluate the efficacy of multiple doses of IMG-007 in AD participants as measured by EASI at Week 12	Percentage change in EASI from baseline to Week 12
Exploratory Objectives	Exploratory Endpoints
To evaluate the efficacy of multiple doses of IMG-007 in AD participants as measured by EASI, IGA, SCORAD index, and patient-assessed itch and sleep quality NRS, PGIS of AD, PGIC of AD, and DLQI	
 Mean and mean % change from baseline in EASI by visit Proportion (%) of participants achieving EASI-50 by visit Proportion (%) of participants achieving EASI-75 by visit Proportion (%) of participants achieving EASI-90 by visit Mean change from baseline in IGA by visit Proportion (%) of participants achieving IGA 0 or 1 (clear or almost clear) and \geq 2-point reduction from baseline by visit Proportion (%) of participants achieving \geq 2-point reduction in IGA from baseline by visit Change from baseline in percent BSA by visit Change from baseline in SCORAD by visit Mean and mean % change from baseline in WI-NRS by visit Proportion (%) of participants achieving a \geq 4-point reduction from baseline in WI-NRS by visit in participants with WI-NRS \geq 4 at Baseline Mean and mean % change from baseline in SQ-NRS by visit Change from baseline in PGIS by visit Proportion (%) of participants with PGIS of 0 or 1 by visit Proportion (%) of participants reporting PGIC of “much better” or “a little better” by visit Change from baseline in DLQI by visit Proportion (%) of participants achieving \geq 4-point reduction from baseline in DLQI by visit in participants with DLQI \geq 4 at Baseline
To further characterize safety and tolerability of multiple doses of IMG-007 in AD participants	
 Incidence of TEAEs by severity and relationship to study treatment Changes from baseline in laboratory parameters, vital signs and ECG parameters by visit Incidence of clinically significant abnormal values in laboratory and ECG parameters by visit

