7.2 Safety Assessments

Safety assessments will include AEs, SAEs, vital signs and physical examination, 12-lead ECG, and laboratory assessments, including pregnancy tests.

Planned timepoints for all safety assessments are listed in the SoA ([Table 1](#)). Additional timepoints for safety tests (e.g., added as necessary per protocol needs) may be added during the study based on newly available data to ensure appropriate safety monitoring.

The investigator/designee will be responsible for determining the clinical significance of any results that fall outside of the laboratory normal ranges.

Every effort will be made to schedule and perform the procedures as closely as possible to the nominal time, considering appropriate posture conditions, practical restrictions, and the other procedures to be performed at the same timepoint.

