7.2.3 Vital Signs and Physical Examination

Vital signs will be measured in semi-supine or supine position after at least 5 minutes of rest and will include respiratory rate, temperature, systolic and diastolic blood pressure, and pulse rate. Vital sign assessments can be repeated at the discretion of the PI or designee.

A complete physical examination will include, at a minimum, assessments of the skin, head and neck, cardiovascular, respiratory, gastrointestinal, and neurological systems. Please refer to the SoA ([Table 1](#)) as to when the assessments are required.

A brief physical examination will include, at a minimum, assessments of the skin, lungs, cardiovascular system, and abdomen (liver and spleen). Symptom-directed physical examinations will be completed at each follow-up visit at the discretion of the investigator.

Investigators will be instructed to pay special attention to clinical signs related to previous serious illnesses. Unscheduled physical examinations can be conducted at the discretion of the PI or designee.

7.2.4 12-Lead Electrocardiogram

The investigator or designee will perform ECG examinations at the timepoints listed in the SoA ([Table 1](#)).

Heart rate and PR, QRS, QT, and QTc intervals, etc., will be measured. Triplicate ECG will be taken if there are any clinically significant abnormalities detected by the physician in a single ECG.

Resting 12-lead ECGs should be recorded after the participant has been semi-supine or supine for a minimum of 5 minutes. ECGs will be interpreted on-site by the investigator to ensure participant safety. The PI (or designee) will evaluate ECG tracings to determine if they are normal, or if there are any clinically significant abnormalities. Site standard ranges will be used to determine if any parameters are considered out of range. ECGs can be repeated at the discretion of the PI or designee.

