HBsAg	Hepatitis B Surface Antigen
hCG	Human Chorionic Gonadotropin
HCV	Hepatitis C Virus
HIV	Human Immunodeficiency Virus
IA	Interim Analysis
ICF	Informed Consent Form
ICH	International Conference of Harmonization
IGA	Investigator's Global Assessment
IMP	Investigational Medicinal Product
IV	Intravenous
LOCF	Last Observation Carried Forward
MAR	Missing At Random
MedDRA	Medical Dictionary for Regulatory Activities
NCS	Not Clinically Significant
NRS	Numerical Rating Scale
OX40L	OX40 Ligand
PD	Pharmacodynamic

PGIC	Patient Global Impression of Change
PGIS	Patient Global Impression of Severity
PK	Pharmacokinetic
PT	Preferred Term
RM	Rescue Medication
RO	Receptor Occupancy
SAE	Serious Adverse Event
SAP	Statistical Analysis Plan
SCORAD	Scoring Atopic Dermatitis
SD	Standard Deviation
SE	Standard Error
SOC	System Organ Class
SQ-NRS	Sleep Quality Numerical Rating Scale
SRC	Safety Review Committee
TARC	Thymus- and Activation-regulated Chemokine
TB	Tuberculosis
TCI	Topical Calcineurin Inhibitors
TCS	Topical corticosteroid
TEAE	Treatment Emergent Adverse Event
TNFR	Tumor Necrosis Factor Receptor
UV	Ultraviolet
Vc	Central Compartment Volume
VS	Vital Sign
WHODrug	World Health Organization Drug Dictionary
WI-NRS	Worst Itch Numerical Rating Scale

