4.6.3 Vital Signs and Physical Examination Variables

The following vital signs (VS) parameters will be collected:

- Weight (kg) and height (cm)
- Systolic and diastolic blood pressure (mmHg)
- Pulse rate (bpm)
- Temperature (C)
- Respiratory rate (breaths/min)

Weight and height will be measured only at baseline. Other vital signs parameters will be collected as specified in the SoA ([Appendix 12.1](#)). On study treatment dosing days, i.e., Baseline (Day 1), Week 2 (Day 15), and Week 4 (Day 29), vital signs should be assessed before initiation of infusion; 15 (\pm 5) minutes after the initiation of the infusion; 15 (\pm 5) minutes after end of infusion (EOI), and 1 hour (\pm 15 minutes) post EOI.

A complete physical examination will include, at a minimum, assessments of the skin, head and neck, cardiovascular, respiratory, gastrointestinal, and neurological systems and the assessment will be performed as specified in the SoA ([Appendix 12.1](#)).

A brief physical examination will include, at a minimum, assessments of the skin, lungs, cardiovascular system, and abdomen (liver and spleen). Symptom-directed physical examinations will be completed at each follow-up visit at the discretion of the investigator.

Investigators will be instructed to pay special attention to clinical signs related to previous serious illnesses. Unscheduled physical examinations can be conducted at the discretion of the PI or designee.

4.6.4 12-Lead Electrocardiogram (ECG) Variables

The following ECG parameters will be collected along with their corresponding clinical significance:

- Heart rate (bpm)
- PR interval (msec)
- QRS interval (msec)
- QT interval (msec)
- QTcB interval (msec)
- QTcF interval (msec)

Triplet ECG will be taken if there are any clinically significant abnormalities detected by the physician in a single ECG. The ECG assessment will be performed at timepoints listed in the SoA ([Appendix 12.1](#)).

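### The SAP has no table of clinically significant laboratory and ECG abnormalities by visit, does not say what stands in for it, and its two-level ECG shift table cannot show worsening within abnormal

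*SAP*

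**What the plan says.** **Protocol.** Section 3, Table 3 includes among the exploratory safety endpoints "Incidence of clinically significant abnormal values in laboratory and ECG parameters by visit". Section 11.3.1 gives the matching analyses. For laboratory data it plans the number and proportion of participants with a "treatment-emergent clinically significant abnormal value based on predefined criteria, and data listings", plus a shift from baseline between normal and abnormal categories by visit. For vital signs and ECG it says "Changes from baseline, number, and proportion of participants with clinically important values will be presented descriptively". The investigator supplies the judgement. Under 7.2.4 the ECG tracings are evaluated to "determine if they are normal, or if there are any clinically significant abnormalities", and under 7.2 the investigator is "responsible for determining the clinical significance of any results that fall outside of the laboratory normal ranges".

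**SAP.** Section 4.6.4 states: "The following ECG parameters will be collected along with their corresponding clinical significance". The abbreviation list defines CS and NCS, the latter as "Not Clinically Significant", but no analysis in section 6 uses either term. Section 6.9.4 gives, by visit, descriptive statistics with change from baseline, "ECG status (i.e., normal, abnormal) summarized by a shift table", and seven notable-finding criteria. Section 6.9.2 gives laboratory values and changes by visit, a shift table of abnormal values over the study, and CTCAE grades for five haematology and four chemistry parameters, taking the worst grade. Section 5, on changes from the protocol, records only the removal of Cohort 2.

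**The concern.** An endpoint named in the protocol should be traceable to an output in the SAP, or the SAP should say that it was dropped or redefined. Here neither happens. No table in 6.9.2 or 6.9.4 is labelled or defined as incidence of clinically significant abnormality.

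The ECG shift table adds a specific loss. The significance judgement is collected and then merged into a single abnormal category. Rhythm and morphology findings are where that judgement matters most, because no interval cut-off captures them. In an early trial whose primary objective is adverse events, a qualitative ECG change that becomes clinically significant on treatment should be visible in the ECG summary itself.

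**Working it through.** No sample-size or power figure bears on this point. The check sets the endpoint against the planned outputs and counts what they cover.

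**1. Endpoint against output**

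| Element | Protocol (Table 3, 11.3.1) | SAP (6.9.2, 6.9.4) |
|---|---|---|
| ECG, clinical significance | Incidence by visit | Not tabulated |
| ECG, thresholds | Clinically important values, n and proportion | Seven criteria by visit: QT (1), QTcF (2), heart rate (2), PR (1), QRS (1) |
| ECG, interpretation | Normal, or clinically significant abnormality (7.2.4) | Normal or abnormal |
| Laboratory, clinical significance | Treatment-emergent, predefined criteria; by visit in Table 3 | Worst CTCAE grade for nine parameters; by visit not stated |
| Laboratory, shift | Normal or abnormal, by visit | Abnormal values during the study |

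**2. What the two-level ECG table merges**

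With three levels (normal; abnormal, not clinically significant; abnormal, clinically significant) there are 3 × 3 = 9 baseline-to-visit transitions. With two levels there are 2 × 2 = 4 cells:

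- normal to normal: 1 transition
- normal to abnormal: 2 transitions, so a new clinically significant finding looks the same as a new insignificant one
- abnormal to normal: 2 transitions
- abnormal to abnormal: 4 transitions, including not significant to significant, which reads as no change

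Check: 1 + 2 + 2 + 4 = 9.

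**3. Laboratory coverage** (SAP 4.6.2 table against 6.9.2)

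- Parameters listed: 15 haematology + 16 chemistry = 31.
- Five white-cell types appear both as a percentage and as a count, so distinct analytes = 31 − 5 = 26.
- CTCAE-graded: 5 + 4 = 9.
- Distinct analytes not graded: 26 − 9 = 17, and 17/26 = 65%.
- Urinalysis: 0 of 10 items graded.

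The ungraded analytes include sodium, potassium, calcium, glucose, alkaline phosphatase and eosinophils. Eosinophils are on the list for CTCAE grading for the safety review committee (SAP 9.2) but not in 6.9.2 or Appendix 12.8.

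**4. How much could be affected**

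The protocol's schedule of assessments and SAP Appendix 12.6 place scheduled post-baseline ECGs at Weeks 12 and 24. With 13 participants that is at most 13 × 2 = 26 scheduled readings. One participant is 1/13 = 7.7% of the cohort.

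**The case against.** The strongest reply is that the endpoint is produced under other names. Protocol 11.3.1 ties laboratory significance to predefined criteria and speaks of clinically important ECG values. CTCAE grades and the notable-finding thresholds are predefined criteria, and Table 3 does not say that significance must be the investigator's judgement. On that reading the ECG part is largely delivered, by visit, and the laboratory part is partly delivered. This reading is reasonable, but the SAP never states it, and it would still leave 17 of 26 blood analytes ungraded and the laboratory grades not stated to be by visit.

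Second, Protocol 8.2.3.1 requires a laboratory, vital-sign or ECG result judged clinically significant to be reported as an adverse event, except where it is unequivocally due to natural disease progression. Such results therefore reach the treatment-emergent adverse event tables, which serve the primary endpoint. This stands and is the main reason the point is minor. It does not replace the endpoint: those tables are by system organ class and preferred term, not by parameter and visit, and sites are told to prefer the clinical term over the laboratory one.

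Third, the two-level laboratory shift follows Protocol 11.3.1. That also stands, and no change to its categories is asked for.

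Fourth, results are listed by participant and visit. This helps in 13 people, but the laboratory listing in 6.9.2 names an abnormal flag and a CTCAE grade, not a significance flag, and the ECG listing does not state its contents.

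A reader might infer that the SAP reports only normal versus abnormal, or that a safety signal has no route to the report. The documents do not support either. The same SAP 6.9.4 list gives change from baseline and seven threshold criteria by visit, 6.9.2 gives CTCAE grades, and the adverse event route remains open.

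**Conclusion.** The gap is real and small. The SAP has no table of clinically significant laboratory and ECG abnormalities by visit and does not say that its notable-findings and CTCAE tables replace one. The two-level ECG shift table cannot separate clinically significant from other abnormalities. Worsening within abnormal is therefore invisible in that table and, for rhythm and morphology, has no other ECG summary. For laboratory data, grading reaches 9 of 26 distinct blood analytes, at worst grade, with by-visit reporting not stated.

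Severity is minor: an exploratory endpoint in one open-label cohort of 13, with listings and adverse event tables alongside.

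The conclusion rests on three assumptions. First, that the protocol version the SAP was written to (V6.0, 05 February 2024) carried the same endpoint; the protocol supplied is dated 14 June 2024, after SAP version 2.0 of 17 May 2024, and the V6.0 wording cannot be seen. If V6.0 lacked the endpoint, silence in section 5 was not an omission when written, but the SAP still needs aligning with the current protocol. Second, that the table shells, which are not supplied, add no significance category. Third, that ECG significance is in the database, as SAP 4.6.4 indicates. For laboratory results the investigator's judgement is required, but no per-result database field is documented, so a demand for significance tables on every laboratory parameter would go beyond what the documents support.

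**What to change.** 1. **SAP 6.9.4:** make the ECG shift table three-level by visit (normal; abnormal, not clinically significant; abnormal, clinically significant), and report n (%) of participants with a clinically significant ECG at each visit. Keep the notable findings as they are.
2. **SAP 6.9.2:** report treatment-emergent abnormalities by visit using the predefined CTCAE criteria, or the investigator's significance flag where it is in the database. Keep the worst-grade table. Settle whether eosinophils are graded, since 9.2 and 6.9.2 differ.
3. **SAP section 5:** state which criteria define the Table 3 endpoint for ECG and for laboratory data, and record any difference from the protocol.

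The cost is a few extra table shells and a short paragraph. The ECG part uses data already collected at two scheduled post-baseline visits. With 13 participants many cells will be zero, which is acceptable for a safety table. No change to trial conduct is needed.
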